6.5.1.3. Asymptomatic SARS-CoV-2 Infection

The incidence of asymptomatic SARS-CoV-2 infection measured by RT-PCR and/or serology tests obtained postbaseline visits counted starting 14 days after the second injection in Part 2 participants with negative SARS-COV-2 status at baseline will be summarized by incidence rate (number of cases divided by the total person-time).

Asymptomatic SARS-CoV-2 infection is identified by absence of symptoms and infections as detected by RT-PCR or serology tests. Specifically:

• Absence of COVID-19 symptoms +/- 14 days from at least one positive test below:

- bAb level against SARS-CoV-2 nucleocapsid protein negative at Day 1 that becomes positive (as measured by ligand-binding assay) postbaseline, OR
- Positive RT-PCR test postbaseline (at scheduled or unscheduled/illness visits)

The date of documented asymptomatic infection is the earlier date of positive serology test result based on bAb specific to SARS-CoV-2 nucleocapsid due to infection, or positive RT-PCR at scheduled visits, with absence of symptoms.

The time to the asymptomatic SARS-CoV-2 infection will be calculated as:

Time to the asymptomatic SARS-CoV-2 infection = Date of asymptomatic SARS-CoV-2 infection test – Date of randomization + 1.

Asymptomatic SARS-CoV-2 infection will be assessed primarily for cases starting 14 days after second injection. COVID-19 may also be assessed for cases starting after first injection, 14 days after first injection, and starting after second injection.

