• To evaluate the immune response against SARS-CoV-2 original strain elicited by mRNA-1273.214 vaccine administered as 2 doses 8 weeks apart in participants aged 12 weeks to < 6 months, compared with the immune responses against original strain induced by mRNA-1273 primary series (100 µg, 2 doses 28 days apart)	GMT of antibodies and SRR against SARS-CoV-2 original strain at 28 days after the second dose of mRNA-1273.214 primary series, compared with GMT and SRR against original strain at Day 57 (28 days after the second dose) in Study mRNA-1273-P301 dosed with mRNA-1273 primary series	
Exploratory Objectives	Exploratory Endpoints	
To evaluate the incidence of COVID-19 after mRNA-1273.214 vaccine administered as 2 doses 8 weeks apart	The incidence of the first occurrence of COVID-19 postbaseline, where COVID-19 is defined as symptomatic disease based on CDC case definition ²	
To evaluate the incidence of SARS-CoV-2 infection after mRNA-1273.214 vaccine administered as 2 doses 8 weeks apart	 The incidence of SARS-CoV-2 infection including symptomatic and asymptomatic infection (by serology and/or RT-PCR) postbaseline SARS-CoV-2 infection will be defined in participants with negative SARS-CoV-2 at baseline: bAb level against SARS-CoV-2 nucleocapsid protein negative at Day 1, that 	
	becomes positive (as measured by ligand-binding assay) postbaseline, OR O Positive RT-PCR postbaseline	
To evaluate the incidence of asymptomatic SARS-CoV-2 infection after mRNA-1273.214 vaccine administered as 2 doses 8 weeks apart	The incidence of SARS-CoV-2 infection measured by RT-PCR and/or bAb levels against SARS-CoV-2 nucleocapsid protein (by ligand-binding assay) postbaseline in participants with negative SARS-CoV-2 at baseline, in the absence of any COVID-19 symptoms	
To characterize the clinical profile and immune responses of participants with COVID-19 or with SARS-CoV-2 infection	Description of clinical severity and immune responses of participants who are identified as infected by SARS-CoV-2 (COVID-19)	

Protocol: mRNA-1273-P206, Original

- To evaluate immune response elicited by the primary series of mRNA-1273.214 against variant(s) of interest
- GMT, SRR, and GMFR of Ab against variant(s) of interest

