WHODD	World Health Organization drug dictionary

1. Introduction

This statistical analysis plan (SAP), which describes the planned analyses for Study mRNA-1273-P206, is based on the most recent approved clinical study protocol (CSP), Original Version, dated 17-Jun-2022 and the most recent approved electronic case report form (eCRF) Version 4.004, dated 09-Mar-2023.

In addition to the information presented in the statistical analysis plan section of the protocol (Section 8) which provides the principal features of analyses for this study, this SAP provides statistical analysis details/data derivations. It also documents modifications or additions to the analysis plan that are not "principal" in nature and result from information that was not available at the time of protocol finalization.

Study mRNA-1273-P206 is a Phase 2, two-part, open-label in Part 1 and observer-blind, randomized, placebo-controlled in Part 2 study to evaluate the safety, tolerability, reactogenicity, and effectiveness of mRNA-1273.214 severe acute respiratory syndrome coronavirus 2 (SARS-CoV-2) vaccine in infants aged 12 weeks to < 6 months.

PPD Biostatistics and Programming team, designee of Moderna Biostatistics and Programming department, will perform the statistical analysis of the safety, tolerability, reactogenicity, and effectiveness data; Statistical Analysis System (SAS) Version 9.4 or higher will be used to generate all statistical outputs (tables, figures, listings, and datasets). If the methods in this SAP differ from the methods described in the protocol, the SAP will prevail.

In this document, subject and participant are used interchangeably; injection of investigational product (IP), injection, and dose are used interchangeably; vaccination group and treatment group are used interchangeably.

2. Study Objectives

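### SAP 6.5.1.3 requires a symptom-free window around only one positive test, so an infant with PCR-confirmed symptomatic COVID-19 soon after Dose 2 can be counted as an asymptomatic infection

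*SAP*

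**What the plan says.** The endpoint is stated in protocol Section 3, Table 3, and repeated in SAP 3.3: infection shown by RT-PCR and/or nucleocapsid antibody "in participants with negative SARS-CoV-2 at baseline, in the absence of any COVID-19 symptoms". Neither statement sets a time limit on the symptoms.

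The derivation is in SAP 6.5.1.3. After a general sentence about absence of symptoms, it gives the specific rule: "Absence of COVID-19 symptoms +/- 14 days from at least one positive test below". Two kinds of test follow. One is nucleocapsid seroconversion: a negative result on Day 1 and a positive one at any later time. The other is PCR, and here illness visits are included: "Positive RT-PCR test postbaseline (at scheduled or unscheduled/illness visits".

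The date rule differs from the definition. Its serology limb reads: "The date of documented asymptomatic infection is the earlier date of positive serology test result based on bAb specific to SARS-CoV-2 nucleocapsid due to infection". Its PCR limb admits only "RT-PCR at scheduled visits, with absence of symptoms". An illness-visit PCR can therefore qualify under the definition but cannot set the date.

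On counting, "Asymptomatic SARS-CoV-2 infection will be assessed primarily for cases starting 14 days after second injection". SAP 6.5.1.1 uses the same primary start for COVID-19. SAP Section 1 states: "If the methods in this SAP differ from the methods described in the protocol, the SAP will prevail".

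**The concern.** Nucleocapsid seroconversion is an interval-censored marker. A sample that is positive at Day 85 after a negative Day 1 does not say when infection occurred, and a known symptomatic episode may explain it. The rule asks only whether symptoms fell near one of the positive tests, so a late serology result can qualify although the PCR that documented the illness does not.

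Nothing in SAP 6.5.1.1 to 6.5.3 makes the COVID-19 and asymptomatic endpoints mutually exclusive, attributes a seroconversion to an earlier known episode, or censors at a prior COVID-19 case. SAP 6.5.2 mentions a censoring time but does not define it.

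The exploratory incidence of asymptomatic infection by arm would then include some symptomatic infections. If the vaccine reduces symptomatic disease, the placebo arm has more such infections to misclassify. The arms could then differ in asymptomatic infection with no true effect on it. The documents give no figures from which to size this.

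**Working it through.** The plan states no figure that depends on this rule, so the check applies the rule literally to a constructed infant.

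**Inputs**

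- Dose 2 is on nominal Day 57 (protocol Table 1).
- The surveillance blood sample is taken on Day 1 and at the Day 85 visit. That visit has a window of -14/+7 days, so the draw can fall from 85 - 14 = Day 71 to 85 + 7 = Day 92 (protocol Table 1; SAP Appendix E).
- The primary window opens 14 days after Dose 2: 57 + 14 = Day 71 (SAP 6.5.1.1 and 6.5.1.3).
- Constructed infant: negative at baseline, symptoms and a positive illness-visit PCR both on day s (s at least 57), nucleocapsid-positive at the draw on day V, no other symptoms.

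**Steps**

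1. The PCR on day s has symptoms 0 days away, so it does not qualify.
2. The serology on day V qualifies if V - s > 14, that is, s ≤ V - 15.
3. The case is dated V, because the date rule passes over the illness-visit PCR. It is in the primary window if V - 57 ≥ 14, that is, V ≥ 71.
4. The illness is a primary COVID-19 case if s - 57 ≥ 14, that is, s ≥ 71.
5. Both counts apply when 71 ≤ s ≤ V - 15.

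| Draw day V | Latest qualifying onset (V - 15) | Onsets classed as asymptomatic | Also primary COVID-19 |
|---|---|---|---|
| 71 | 56 | none from Day 57 on | none |
| 85 | 70 | Days 57 to 70 | none |
| 92 | 77 | Days 57 to 77 | Days 71 to 77 |

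**Example.** Take s = 62 and V = 85. The gap is 85 - 62 = 23 days, which exceeds 14, so the serology qualifies. The case is dated Day 85, which is 85 - 57 = 28 days after Dose 2 and inside the primary window. The illness itself is 62 - 57 = 5 days after Dose 2, before the primary COVID-19 window opens. In the primary analyses this infant would appear only as an asymptomatic infection.

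**Alternative rule.** If the symptom-free window must hold around every positive test, step 1 disqualifies the infant. No onset day is then classed as asymptomatic for a draw on Day 71, 85 or 92.

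**Sensitivity to the simplifications.** If symptoms persist, s in step 2 is the last symptomatic day, so fewer onsets qualify. SAP 6.5.1.1 dates a COVID-19 case by the later of symptoms and PCR. Brief symptoms on Day 70 swabbed on Day 72 would therefore be a primary COVID-19 case (72 - 57 = 15) and, with a Day 85 draw, also an asymptomatic case (85 - 70 = 15). The absence of overlap at Day 85 assumes a same-day swab.

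**The case against.** The best defense is that the SAP means something narrower. The same section speaks generally of absence of symptoms, and repeats it in the date rule. The phrase about at least one positive test may only introduce the serology-or-PCR list. The 14-day link mirrors the pairing of symptoms and PCR in SAP 6.5.1.1. This has some force: the accurate claim is that such an infant can be counted under the literal rule, not that the sponsor intends it. It does not remove the point, because the 14-day condition is given as the specific form of the definition and is what a programmer would code. The precedence clause does not settle it either, since SAP 3.3 carries the same unrestricted endpoint as the protocol.

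Four stronger readings are tempting and are not supported:

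- **A large error rate.** Of the 84 days from Day 1 to Day 85, the look-back covers 14, leaving 70 (70/84 = 83%). That is a share of unchecked days, not a misclassification rate. Infants with PCR-confirmed symptomatic infection before Dose 2 should have that dose delayed about 90 days (protocol 7.1.1) and would usually leave the PP Set. Symptomatic infants never swabbed depend on missed surveillance, because protocol 8.9.3 calls for an illness visit.
- **Routine double counting.** At a nominal Day 85 draw with a same-day swab, the primary windows do not overlap. Double counting needs a late draw, a lagging swab near Day 71, or the optional windows that start earlier. Extending it to Day 237 assumes nucleocapsid testing of that sample. The assay list permits this, but the surveillance sample and the serology rows of SAP Appendix B cover only Days 1 and 85.
- **The same error in the FAS.** SAP 6.5.2 illustrates its FAS event count only with COVID-19 cases. SAP 6.5.3 applies the mITT and mITT-1 Sets to key efficacy endpoints without saying that asymptomatic infection is one.
- **That symptoms should be barred over the whole seroconversion interval.** That interval contains both injections. Protocol 8.9.3 notes that COVID-19 symptoms overlap with solicited reactions, and Table 7 solicits fever and loss of appetite. Protocol 2.3.2 reports more solicited reactions with vaccine than placebo in two earlier studies. Such a rule could remove more true asymptomatic cases from the vaccine arm.

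**Conclusion.** The point holds as a conflict between the derivation and its own endpoint. Under the literal rule, symptomatic PCR-confirmed illness on Days 57 to 70 can become an asymptomatic case at a Day 85 draw. The range is Days 57 to 77 for a Day 92 draw, and empty for a Day 71 draw. These are ranges of onset days, not numbers of infants: the documents give neither infection rates nor seroconversion probabilities. The ranges assume Dose 2 on Day 57, symptoms and swab on the same single day, and seropositivity by the draw.

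The consequence is limited. The endpoint is exploratory and Part 2 only. It is summarized as incidence rates with exact Poisson intervals, with no hypothesis and no planned between-arm test. The co-primary immunogenicity conclusions do not depend on it. Any bias between arms is directional and unquantified. SAP Section 7 records an enrollment pause during Part 1, so the point matters only if Part 2 is run.

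**What to change.** In SAP 6.5.1.3:

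1. Replace the condition on one positive test with: no COVID-19 symptoms within 14 days before or after every positive RT-PCR or nucleocapsid test up to and including the asymptomatic case date. Stopping at the case date keeps a later symptomatic reinfection from erasing a true earlier asymptomatic case.
2. Do not count as asymptomatic an infant who met the COVID-19 case definition on or before that date. State that this applies to any postbaseline case, including one before the primary window opens; otherwise onsets on Days 57 to 70 would escape this exclusion.
3. Make the date rule agree with the definition on illness-visit PCR. At present an infant whose only positive is an unscheduled PCR can meet the definition and have no event date.

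A symptom-free requirement over the whole seroconversion interval should be at most a sensitivity analysis, and should exempt symptoms in the 7-day solicited period after each injection.

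The cost is SAP wording, a programming change and slightly fewer asymptomatic cases. Symptom, PCR and serology dates are already collected. These changes remove the PCR-confirmed error. They do not reach a symptomatic infection that was never swabbed and fell more than 14 days before the draw; the sensitivity analysis would show how much that matters.

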6.5.2. Analysis Method

The number and percentage of subjects who had an event (i.e., COVID-19 case) will be summarized for the PP set, and FAS.

The incidence rate will be calculated as the number of cases divided by the total persontime (person-year or person-month). The 95% CI of the incidence rate will be calculated using the exact method (Poisson distribution) and adjusted by person-time.

Person-time is defined as the total time from randomization date in Part 2 to the date of event, last date of study participation, censoring time, or efficacy data cutoff date, whichever is earlier.

Descriptive summaries of clinical profile and immunologic endpoints to characterize participants with COVID-19 or SARS-CoV-2 infection during the study will also be provided.

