- Imputation rules for missing AE dates are provided in Appendix D.
- For laboratory assessments, if majority of results are indefinite, imputation of these values will be considered. If the laboratory results are reported as below the LLOQ (e.g., <0.1), the numeric values will be imputed by 0.5 × LLOQ in the summary. If the laboratory results are reported as greater than the ULOQ (e.g., >3000), the numeric values will be imputed by ULOQ in the summary.
- Other incomplete/missing data will not be imputed, unless specified otherwise.

Treatment groups:

The following vaccination groups will be used for summary purposes:

- Part 1, Open-Label Phase:
 - o mRNA-1273.214 5 μg
 - o mRNA-1273.214 10 μg
 - o mRNA-1273.214 Total
- Part 2, Blinded Phase:

Treatment in Part 2 will be the selected dose level from Part 1 or Placebo

- o mRNA-1273.214 5 μg, or
- o mRNA-1273.214 10 μg

And

o Placebo

Subjects who received at least one dose of mRNA-1273.214 in Part 2 will be included in the mRNA-1273.214 selected dose level group (as actual treatment) in Part 2 in the safety and immunogenicity analyses.

External comparator:

• Comparator: mRNA-1273 100 μg primary series (from study P301 in young adult participants (18-25 years) who received 2 doses of mRNA-1273 primary series)

Summary by study part:

Separate shells will be provided for Part 1 and Part 2 of the study. All analyses and data summaries/displays will be provided by vaccination group.

Analysis Periods

The following analysis periods and treatment groups will be used for efficacy or immunogenicity analyses for Part 2, the blinded phase, unless specified otherwise:

Part 2 Group	Description	Part 2 Blinded Phase Analysis Period for Efficacy or Immunogenicity
mRNA-1273.214	Participants randomized to mRNA-1273.214 in the Blinded Phase	From randomization to earliest date of unblinding (inclusive), study

Diagram	Participants randomized to	discontinuation, study completion,
Placebo	Placebo in the Blinded Phase	death, and data cutoff date

The following analysis period and treatment groups will be used for safety analysis for Part 2, the blinded phase, unless specified otherwise:

Part 2 Group	Description	Part 2 Blinded Phase Analysis Period for Safety
mRNA-1273.214	Participants received at least one dose of mRNA-1273.214 in the Blinded Phase	From the date of first injection to the earliest date of unblinding (inclusive),

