6.5.1. Endpoint Definition/Derivation

6.5.1.1. CDC Case Definition of COVID-19

The incidence of the first occurrence of COVID-19 postbaseline, where COVID-19 is defined as symptomatic disease based on CDC case definition, starting 14 days after each injection of mRNA-1273.214, will be summarized using incidence rate (number of cases divided by the total person-time).

Cases are defined as participants meeting clinical criteria based on both symptoms for COVID-19 and positive RT-PCR test results.

A positive PCR result of the eligible symptoms are summarized below in Table 1.

Table 1 Derivation for CDC Case Definition of COVID-19

	COVID-19
Postbaseline PCR results	Positive, AND
Systemic Symptoms	at least ONE of the following systemic symptoms: Fever (temperature $\geq 38^{\circ}$ C/ $\geq 100.4^{\circ}$ F) or chills (of any duration, including ≤ 48 hours), fatigue, headache, myalgia, nasal congestion or rhinorrhea, new loss of taste or smell, sore throat, abdominal pain, diarrhea, nausea/vomiting, poor appetite/poor feeding; OR
Respiratory symptoms	at least ONE of the following respiratory signs/symptoms: cough (of any duration, including ≤ 48 hours), shortness of breath or difficulty breathing (of any duration, including ≤ 48 hours).

The date of documented CDC Case Definition of COVID-19 (case) will be the later date of ([systemic symptom reported, or respiratory symptom reported] and, [date of positive PCR test]). Specifically, the date of documented CDC Case Definition of COVID-19 will be the

later date of the following two dates (date of positive PCR test, and the date of eligible symptom(s)), and the two dates should be within 14 days of each other.

- Date of positive PCR test,
- Date of eligible symptom(s), defined as earliest of
 - Respiratory symptom: earliest date of an eligible respiratory symptom is reported
 - Systemic symptoms: earliest date of the eligible systemic symptom is reported

The time to the first occurrence of CDC Case Definition of COVID-19 will be calculated as:

Time to the first occurrence of CDC Case Definition of COVID-19 = Date of documented CDC Case Definition of COVID-19 – Date of Randomization + 1.

COVID-19 will be assessed primarily for cases starting 14 days after second injection, i.e. date of documented COVID-19 – Date of the 2^{nd} injection \geq 14. COVID-19 may also be assessed for cases starting after first injection, 14 days after first injection, and starting after second injection.

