6.5.1.2.SARS-CoV-2 Infection or COVID-19 regardless of symptomatology or severity

The incidence of SARS-CoV-2 infection starting 14 days after each injection of mRNA-1273.214 will be summarized using incidence rate (number of cases divided by the total person-time).

SARS-CoV-2 infection will be defined in participants with negative SARS-CoV-2 at baseline:

- Ab level against SARS-CoV-2 nucleocapsid protein that is negative at Day 1, but becomes positive (as measured by ligand-binding assay) postbaseline, OR
- Positive RT-PCR postbaseline.

Derivation of SARS-CoV-2 Infection is summarized in Table 2 below.

Table 2 Derivation for SARS-CoV-2 Infection

	Postbaseline assessments	

Baseline SARS- CoV-2 Status		bAb levels against SARS-CoV-2	Endpoint: SARS-CoV-2
	PCR test post baseline	Nucleocapsid	infection
	Positive (either at nasal swab test, or at symptom-prompt		
Negative at Baseline	nasal swab test)		Case
		Positive (at Post	
		baseline visit or	
		later) as measured	
		by ligand-binding	
Negative at Baseline		assay	Case

The incidence rate will be calculated as the number of cases divided by the total persontime.

The date of documented infection will be the earlier of:

- Date of positive postbaseline RT-PCR result, or
- Date of positive serology test result based on bAb specific to SARS-CoV-2 nucleocapsid

Time to the First SARS-CoV-2 infection = Date of the First documented infection - Date of randomization + 1.

SARS-CoV-2 infection regardless of symptomatology and severity will be assessed primarily for cases starting 14 days after second injection. SARS-CoV-2 infection may also be assessed for cases starting after first injection, 14 days after first injection, and starting after second injection.

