6.5.3. Sensitivity and Subgroup Analysis

Sensitivity analysis for key efficacy endpoints will be performed with the same methods described above based on the mITT Set and mITT-1 Set, with cases counted starting from randomization in Part 2. A sensitivity analysis will be performed based on a modified version of the endpoint definition, including COVID-19 non-RT-PCR tests.

Subgroup analysis may be done for the following subgroups:

- Sex (male, female)
- SARS-CoV-2 status at baseline
- Maternal COVID-19 vaccine status
- Maternal COVID-19 infection status
- Breastfeeding history
- Race
- Ethnicity

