9.2. Appendix B: Analysis Visit Windows for Analysis

Safety and Immunogenicity Analysis will be summarized using the following analysis visit window for post injection assessments:

Step 1: If the safety and immunogenicity assessments are collected at scheduled visit, i.e. nominal scheduled visit, the data collected at scheduled visit will be used.

Step 2: If the safety and immunogenicity assessments are not collected at the scheduled visit, assessments collected at unscheduled visit will be used using the analysis visit windows described in Table 3 below.

If a subject has multiple assessments within the same analysis visit, the following rule will be used:

- If multiple assessments occur within a given analysis visit, the assessment closest to the target study day will be used.
- If there are 2 or more assessments equal distance to the target study day, the last assessment will be used.

Table 3 Visit Window

Visit	Target Study Day	Visit Window in Study Day									
Nasal Swabs for SARS	Nasal Swabs for SARS-CoV-2										
Day 1	1 (Date of First Injection)	1, Pre-first-dose									
Day 57 (Month 2)	57 (Date of Second Injection)	[2, 71]									
Day 85 (Month 3)	85	[72,161]									
Day 237 (Month 8)	237	[162, 330]									
Day 422 (Month 14)	422	≥331									
SARS-CoV-2 Serology	7										
Day 1	1 (Date of First Injection)	1, Pre-first-dose									
Day 85 (Month 3)	85	≥2									
Immunogenicity											
Day 1	1 (Date of First Injection)	1, Pre-first-dose									
Day 85 (Month 3)	85	[2,161]									
Day 237 (Month 8)	237	[162, 330]									
Day 422 (Month 14)	422	≥331									

9.3. Appendix C: Imputation Rules for Missing Prior/Concomitant Medications, Non-Study Vaccinations, and Maternal Prior/Concomitant Medications

Imputation rules for missing or partial medication start/stop dates are defined below:

- 1. Missing or partial medication start date:
 - If only Day is missing, use the first day of the month, unless:
 - The medication end date is after the date of first injection or is missing AND the start month and year of the medication coincide with the start month and year of the first injection. In this case, use the date of first injection
 - If Day and Month are both missing, use the first day of the year, unless:
 - The medication end date is after the date of first injection or is missing AND the start year of the medication coincide with the start year of the first injection. In this case, use the date of first injection

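### The SAP counts primary COVID-19 and infection cases from 14 days after Dose 2 but starts person-time at randomization, so for on-schedule completers the incidence rates and exact Poisson limits are 16.6% too low

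*SAP*

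**What the plan says.** **Numerator.** SAP 6.5.1.1 states that "COVID-19 will be assessed primarily for cases starting 14 days after second injection". SAP 6.5.1.2 and 6.5.1.3 set the same primary window for SARS-CoV-2 infection and for asymptomatic infection. Other starting points (after the first injection, 14 days after it, after the second injection) may also be used.

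**Denominator.** SAP 6.5.2 defines the incidence rate as cases over total person-time, with an exact Poisson interval scaled by that same person-time. It gives one definition: "Person-time is defined as the total time from randomization date in Part 2 to the date of event", last participation, censoring or data cutoff, whichever comes first.

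**Related clocks.** The time-to-event formulas in 6.5.1.1 to 6.5.1.3 all subtract the randomization date. In SAP 6.1 the blinded-phase period for efficacy runs "From randomization to earliest date of unblinding (inclusive), study" discontinuation, completion, death or data cutoff. No section moves the start of the clock for the window after Dose 2.

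**Where the clocks do match.** SAP 6.5.3 plans mITT and mITT-1 sensitivity analyses "with cases counted starting from randomization in Part 2". Numerator and denominator then start together.

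**The concern.** A person-time rate estimates incidence only if every day in the denominator is a day on which a countable case could occur. Here the first ten weeks on schedule cannot produce a primary case, yet they are counted as time at risk. The reported figure is therefore not the incidence in the period it is labelled with. Because the exact Poisson limits are divided by the same person-time, the interval shifts down with the point estimate and gives no sign of the problem.

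The SAP also does not say what happens to a participant whose first event falls before the window opens. Under the text as written, that infant could contribute only time in which no primary case was possible.

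At stake are the absolute incidence rates by arm, which are the planned output for these endpoints in Protocol 9.5.3 and SAP 6.5.

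**Working it through.** The documents give no incidence rate, event count or person-time total for these endpoints, so there is no stated figure to reproduce. The schedule they rest on is consistent: Day 57 + 365 = Day 422.

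**Inputs**
- Randomization on Day 1 (Protocol 8.5).
- Dose 2 on Day 57; last visit on Day 422, 365 days after Dose 2 (Protocol 1.3, Table 1).
- Dose 2 visit window −14/+7 days (Table 1), extendable to +14 (footnote 4) and to +21 after a study pause (Protocol 7.4).
- Primary counting starts 14 days after Dose 2 (SAP 6.5.1.1 to 6.5.1.3).
- Person-time starts at randomization (SAP 6.5.2).

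**On-schedule completer**
- Window opens: 57 + 14 = Day 71.
- Time before the window: (57 − 1) + 14 = 70 days.
- Person-time under the SAP: 422 − 1 = 421 days. Aligned person-time: 421 − 70 = 351 days.
- Understatement: 70/421 = 16.6%. Aligned over reported: 421/351 = 1.20.

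**Other permitted Dose 2 days, each followed 365 days after Dose 2**

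| Dose 2 day | Days before window / total | Understatement |
|---|---|---|
| 43 | 56/407 | 13.8% |
| 57 | 70/421 | 16.6% |
| 64 | 77/428 | 18.0% |
| 71 | 84/435 | 19.3% |
| 78 | 91/442 | 20.6% |

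**Shorter follow-up, Dose 2 on Day 57**
- Ending Day 330: 70/329 = 21.3%.
- Ending Day 237: 70/236 = 29.7%.
- Uniform dropout of 10% or 20% (assumed): 70/(70 + 351 × (1 − d/2)) = 17.4% or 18.1%.

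**Events that end person-time.** Assume a constant hazard h that gives an attack rate of 10% or 30% over 421 days.
- Infants with an early first event left out altogether: 70/(70 + (1 − exp(−351h))/h) = 17.2% or 18.7%.
- Infants with an early first event censored at it: 1 − exp(−70h)(1 − exp(−351h))/(1 − exp(−421h)) = 17.4% or 19.2%.

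**Effect on the interval.** Take 255 completers (300 less 15%) and 20 primary cases, both assumed, each infant contributing full follow-up.
- As written: 255 × 421/365.25 = 293.9 person-years; 6.80 per 100 person-years (95% CI 4.16 to 10.51).
- Aligned: 255 × 351/365.25 = 245.1 person-years; 8.16 (4.99 to 12.60).
- The rate and both limits differ by the same factor, 351/421 = 0.834.

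**Between-arm ratio.** None is planned. If one were formed, a true ratio of 0.50 with placebo hazards of 0.2, 0.4 or 0.8 per person-year (assumed) would be read as 0.504, 0.509 or 0.518.

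**The case against.** The strongest reply is that little depends on this. The endpoints are exploratory and descriptive, no ratio or test between arms is planned, and both arms are diluted by nearly the same factor. Case counts and percentages do not use person-time, and the from-randomization mITT and mITT-1 rates are correctly aligned. SAP 7 records an enrollment pause with 18 infants in Part 1 Arm 2, so Part 2 may never supply data. All of this stands and limits the consequence. It does not repair the rates and intervals that the SAP says will be reported. Nor does the mention of censoring time in 6.5.2 help, since it is one of the listed ends of person-time, not a start.

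A reader might infer more than the documents support:

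- **A spurious contrast between doses.** SAP 6.5.1.1 speaks of cases "starting 14 days after each injection of mRNA-1273.214", which suggests that the two 14-day windows will be set side by side with different dilution. The same section then says that the window after the first injection may be assessed, so the documents do not establish that both rates will be reported.
- **A numerator filled with earlier infections.** SAP 6.5.1.2 can date an infection by its positive serology sample, so one acquired before Day 71 could be dated inside the window. How often cannot be sized: the documents give no PCR detection rate, and they are unclear on which nucleocapsid samples beyond Day 1 and Day 85 count. Requiring a negative sample after the window opens would remove every serology-only infection from the primary window if Day 85 is the last sample used.
- **Symptomatic cases counted as asymptomatic.** The bullet "Absence of COVID-19 symptoms +/- 14 days from at least one positive test below" can be read that way, but the surrounding sentences in 6.5.1.3 define the endpoint by absence of symptoms. This is at most a request for clarification, separate from the person-time error.

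**Conclusion.** The mismatch is in the current SAP text and affects all three primary-window endpoints. For participants given Dose 2 on Day 57 and followed to Day 422, each incidence rate and both Poisson limits are 16.6% too low. That figure follows from the schedule alone, but it is not a constant. It is 13.8% to 20.6% over the permitted Dose 2 days if everyone is followed 365 days after Dose 2. That range is not a bound: cutoff, unblinding or dropout makes the shortfall larger. The figures describe the denominator error for cases as the SAP dates them.

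A reader might conclude that the vaccine-versus-placebo comparison is biased. The documents plan no such ratio, and with similar follow-up in both arms it would hardly move. The error concerns absolute rates and their intervals, in an exploratory analysis that matters only if Part 2 is run. It is still worth correcting, because the rule as written gives a wrong rate and the remedy is nearly free.

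**What to change.** In SAP 6.5.1 and 6.5.2:

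- Start person-time and time-to-event at the opening of each case-counting window. For the primary window this is 14 days after the second injection.
- Include only participants still under follow-up and event-free when the window opens. A participant whose first event is earlier leaves that window's numerator and risk set.
- Keep the randomization start only for the from-randomization analyses in 6.5.3.
- Bring the efficacy analysis period in SAP 6.1 into line, so that it does not restore the randomization start.

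The exact Poisson method can stay. The cost is SAP wording and minor reprogramming, with no new data or visits.
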